#### 5.2. **REPORTING PROCEDURES**

All adverse events should be reported. Depending on the nature of the event the reporting procedures below should be followed. Any questions concerning adverse event reporting should be directed to the Chief Investigator in the first instance.

#### 5.3.1 Non serious AEs

All such events, whether expected or not, should be recorded- it should be specified if only some non-serious AEs will be recorded, any reporting should be consistent with the purpose of the trial end points.

Potential AEs and known complications:

Procedure	Known complications
n/a	n/a

#### 5.3.2 Serious AEs

An SAE form should be completed and emailed to the Chief Investigator within 24 hours. However, relapse and death due to asthma and hospitalisations for elective treatment of a pre-existing condition do not need reporting as SAEs.

All SAEs should be reported to the London-Bloomsbury REC where in the opinion of the Chief Investigator, the event was:

- 'related', ie resulted from the administration of any of the research procedures; and
- 'unexpected', ie an event that is not listed in the protocol as an expected occurrence

Reports of related and unexpected SAEs should be submitted within 15 days of the Chief Investigator becoming aware of the event, using the NRES SAE form for non-IMP studies. The Chief Investigator must also notify the Sponsor of all related and unexpected SAEs.

Local investigators should report any SAEs as required by their Local Research Ethics Committee, Sponsor and/or Research & Development Office.

Contact details for reporting SAEs [contact] CI email (and contact details below) Please send SAE forms to: [name] [contact] [name] / Email: [contact] (Mon to Fri 09.00 – 17.00)

### 6. ASSESSMENT AND FOLLOW-UP

The following data will be collected at each study visit.

	Study	Study	Study
	visit 1	visit 2	visit 3
	(0wks)	(12wks)	(24wks)
Study enrolment			
(1) Participant informed consent (and assent from CYP) (n=50)	Х		
(2) Information and provision of Hailie® device (n=50)	Х		
(3) Randomisation to intervention (n=25) or to control group (n=25)	Х		
Inhaler technique	Х	Х	Х
Asthma UK Action plan	Х		
Demographic information	Х		
Asthma characteristics/history	Х	Х	Х
Control group (n=25)			
Electronic monitoring device (programmed with morning and			
evening reminders)			

Financial incentives-based group (n=25)			
Electronic monitoring device (programmed with morning and			
evening reminders)			
Financial incentives (with in-app totaliser, in-app messages		→	
recording progress and in-app traffic light calendar)			
Asthma measures			
(1) ICS adherence %	-	Х	Х
(2) Asthma control (ACT)	Х	Х	Х
(3) Exhaled nitric oxide (FENO)	Х	Х	Х
(4) Self-report adherence (MARS)	Х	Х	Х
Behavioural/psychological measures			
(1) Habit (SRBAI)	Х	Х	Х
(2) Belief in Medicines Questionnaire (BMQ)	Х	Х	Х
(3) Brief illness Perceptions Questionnaire (B-IPQ)	Х	Х	Х
(4) Autonomous/Controlled motivation (adapted from TSRQ)	Х	Х	Х

#### **Incidental findings**

We don't anticipate there to be any incidental findings within this study. However, in the event of any incidental findings, the research team will inform the participant (and their parent/guardian) and will encourage them to inform and discuss findings with their GP. The summary of results from each study visit will also be sent to the GP after each study visit.

#### **Study completion**

Study end is defined as once all contactable participants have had their third and final research visit (the last research visit of the last subject recruited) and completion of the final focus groups for those involved.

All data will be stored for 10 years following completion of the study. At study completion, participants will continue to receive their usual care.

#### Follow-up contact

No further contact from the research team directly related to this study is anticipated following completion. Participants will continue to receive their routine care as per prior to enrollment in this project.

Research Governance and Integrity Team

IRAS: 306829 Version 8.0, Date: 16.01.2023 © Imperial College of Science, Technology and Medicine

### 7. STATISTICS AND DATA ANALYSIS

#### 7.1 Data management

Data entry will be collected by the study coordinator ([name]) and the data analysis will be conducted by the study coordinator with assistance from the chief Investigator ([name]).

All collected data will be entered onto an electronic database (REDCap/Excel) held on a secure Imperial College London server.

#### 7.2 Statistical methods and sample size

As this is a pilot study, a formal sample size calculation is not required. However, the estimated sample size of 50 participants in total is based upon a calculation from unpublished adherence data obtained from Royal Brompton Hospital from 400 children. Mean adherence in the sample was 65% (SD 22%). A Cochrane review of adherence interventions to ICS for asthma found that electronic trackers or reminders led to better adherence of 19% (95% CI 14.47 to 25.26). Based upon this information, to give 80% power to achieve a 19% difference between the intervention group and controls, 21 participants are required per group. The target of 25 per group accounts for participant dropout. This is supported by evidence that as a pilot study, 25 participants per group, with a total of 50 participants is sufficient.

Data analysis will be conducted using the Statistical Package for the Social Services (SPSS). Statistical analysis of quantitative, normally distributed data will be reported with means ± standard deviations (SD) and non-parametric data will be reported as medians with interquartile range. Data will be tested for normality using visual inspection, histograms, and Kolmogorov-Smirnov testing. Parametric tests will be used where possible for normally distributed data and logarithmically transformed data, otherwise appropriate non-parametric tests shall be used. The significance levels for all tests will be set at <0.5.

Categorical data will be reported as proportions. Comparative analysis of variance between 2 groups for continuous data will be performed using the student's t test for normally distributed data and the Mann Whitney U tests for non-normally distributed data and for more than 2 groups the ANOVA or Kruskal Wallis respectively. A comparison of the proportions between groups will be performed using the Pearson Chi 2 tests. Within group analysis the ANOVA test will also be used.

Questionnaire data will be used alongside group comparisons to observe any notable changes or differences between groups.

Qualitative data obtained from the focus groups will be thematically analysed. An independent researcher will aid with the facilitation/analysis of qualitative aspect of the study to ensure there is no bias.

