#### 2.2 Objectives

- 1. To recruit children and young people aged between 11-17 years with asthma and measure adherence using EMDs (programmed with reminders) and a self-report measure (MARS-A) during a 12-week intervention period when financial incentives are given and compare to a group given an EMD (programmed with reminders) only, and to continue to measure adherence during a subsequent 12-week period (when no financial incentives are given) to assess whether financial incentives lead to continued better adherence in the short-medium term compared to the control group.
- 2. To measure asthma outcomes (number of severe exacerbations, time to exacerbation, asthma symptoms and if feasible given COVID-19 constraints, exhaled nitric oxide) at baseline, 12-weeks, and 24-weeks to assess whether financial incentives lead to short-medium term changes in a range of asthma control measures compared to the control group.
- To measure habit (using the self-report behavioural automaticity index, SRBAI) and autonomous/controlled motivation (using a questionnaire adapted from the Treatment Self-Regulation Questionnaire (TSRQ)) at baseline, 12-weeks, and 24-weeks to

Research Governance and Integrity Team

assess whether financial incentives lead to short-medium term changes in medication taking habits and motivations compared to the control group.

- 4. To measure beliefs in medicine (using Beliefs in Medicines Questionnaire, BMQ) and perceptions of illness (using the Brief-Illness Perceptions Questionnaire, B-IPQ) at baseline, 12-weeks, and 24-weeks to assess whether financial incentives lead to short-medium term changes in beliefs and perceptions regarding medication and illness and compared to the control group.
- 5. To conduct focus groups with participants from both the intervention and the control group and interviews with parents/guardians using a topic guide to obtain feedback of the trial and inform the design of a larger RCT.

Research Governance and Integrity Team

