Fifty participants will be enrolled in the 24-week programme and will be randomly assigned to either the financial incentives-based intervention group or the control group using the online service Sealed Envelope™ which will allocate participants to each group on a 1:1

Research Governance and Integrity Team

basis. Participants will be told which group they have been randomly assigned to during study visit 1.

For all participants, there will be a total of 3 study visits: at baseline (0-weeks), at 12-weeks and at 24-weeks. All study visits will take place at the Children's Clinical Research Facility (CCRF) at St Mary's Hospital, Imperial College Healthcare NHS Trust. Due to the continued COVID-19 restrictions, remote study visits will be offered to participants through Microsoft Teams (joining link will be sent to parents electronically) and an option for study visits to be conducted (by the study coordinator) at participant's homes will also be available, if necessary. However, due to financial constraints, we would not be able to perform FENO remotely, so it will be removed as a secondary outcome measure in this event. All study visits will include the collection of asthma-related clinical data, questionnaire data and adherence data which will be described in detail below.

All CYP's GP's will be informed of the CYP's involvement in the study and a summary of results from each study visit will be sent to the CYP's GP. Information shared in this summary will include ACT score, FENO and adherence data. This summary will also be sent to parents. It is important to note that the study team will not be managing the CYP's asthma or intervening if their adherence is poor – this will be made clear to parents/guardians and CYP and it will be suggested they contact their GP or asthma nurse if there are any concerns throughout the study.

All CYP will be issued with an EMD (Hailie® sensor, Adherium, New Zealand) which attaches to their usual inhalers to electronically record inhaler actuation to provide % adherence data.

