All CYP will be required to download the Hailie® associated app on their smartphones and to sync their Hailie® sensor with the associated app, via Bluetooth. The Hailie® sensor will detect medication usage from the attached preventer inhaler and send this to the Hailie® associated app on the CYP's smartphone, also via Bluetooth. The Hailie® associated app will then automatically upload (via WIFI/data connection) the medication usage data to the secure cloud-based Hailie® web portal where the research team will be able to view the data (see image below).

Wi-Fi connection

All CYP will regularly charge and sync their Hailie® device to ensure all data are collected accurately, they will be prompted to do this throughout the study through app notifications. Parents/guardians/CYP will be asked to inform a member of the study team if there are any issues with their EMDs so this can be sorted as soon as possible.

All CYP's Hailie® devices or smartphones will be programmed with both morning and evening audio-visual reminders across the 24-week period. CYP will choose the time of their reminders which will be recorded by the researcher.

There will be no covert adherence monitoring and CYP's adherence data will be downloaded and viewed by the study coordinator before/at each study visit (study visit 2, 12-weeks and study visit 3, 24-weeks). For those in the intervention group, adherence data will also be downloaded and viewed at 4-weeks, 8-weeks to calculate reward amount given only.

At the end of the 24-week programme, all participants will be invited to join a focus group discussion (which will either be in-person at the CCRF or virtually via Microsoft teams) with other CYP from the study. There will be up to 10 participants per focus group and numbers will be dependent upon participant availability. Focus groups with participants from the intervention group and with participants from the control group will be conducted separately. Focus groups will be optional for participants. Parents/guardians will also be invited to take part in an interview in person / via email or telephone to obtain their feedback about the programme. These interviews will be optional and will last approximately 45minutes.

Research Governance and Integrity Team

Interviews will be conducted at study visit 3 and will be conducted in person or virtually (via telephone or via Microsoft Teams, dependent upon preference).

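### The 80% power statement borrows a 19-point effect of trackers or reminders, which both arms receive, and gives no expected effect for the incentive package actually being compared

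*Combined protocol and SAP*

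**What the plan says.** Section 7.2 (Statistical methods and sample size) says that a pilot needs no formal calculation, then bases the 50 participants on one. The variability comes from unpublished data on 400 children at one hospital: "Mean adherence in the sample was 65% (SD 22"%). The effect comes from a Cochrane review of adherence interventions: "electronic trackers or reminders led to better adherence of 19% (95% CI 14.47 to 25.26"). From these it concludes: "to give 80% power to achieve a 19% difference between the intervention group and controls, 21 participants are required per group". The number is raised to 25 for dropout, and pilot-size guidance is cited as further support that "25 participants per group, with a total of 50 participants is sufficient". The sample size text states no alpha; later in the section the plan says "The significance levels for all tests will be set at <0.5".

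On what the arms receive, section 3 (Study design) says "All CYP will be issued with an EMD" and that devices or phones will be "programmed with both morning and evening audio-visual reminders across the 24-week period". The control group gets usual care plus these reminders, and objective 1 in section 2.2 describes the comparison the same way: "compare to a group given an EMD (programmed with reminders) only". What only the intervention arm gets, for the first 12 weeks, is the payments, the in-app totaliser, progress messages and the traffic-light adherence calendar (section 3, and the schedule in section 6).

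**The concern.** The effect used for power should be the effect expected for the randomised contrast. Here the contrast is incentives plus reminders against reminders alone, while the 19 points describe trackers or reminders, which are common to both arms. Whatever the sensor and reminders do for adherence should largely cancel in the between-group difference.

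Nothing else in the documents fills the gap. Section 1.2 cites two earlier asthma studies, but both combined reminders with incentives, neither is described as having a control group, and no numeric adherence effect is given for either. In the team's own feasibility study there was no significant overall change.

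This is the only power statement in the plan, and aim 1 in section 2.1 is effectiveness. A reader would take the trial to have 80% power for incentives against a reminder-only control and could read a non-significant result as evidence that incentives do not work. Aim 3 feeds the pilot into the power calculation of a definitive trial, so the same misplaced effect could be carried forward.

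**Working it through.** **Inputs.** From section 7.2: difference 19 points, SD 22 points, power 80%, 21 per group before dropout and 25 after. From section 3: 1:1 allocation. Alpha and sidedness are not given with the calculation, so they are inferred below.

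**1. Reproduce the plan's figure** (normal approximation, two-sided 0.05):

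n per group = 2 × [SD × (z₀.₉₇₅ + z₀.₈₀) / difference]² = 2 × [22 × (1.960 + 0.842) / 19]² = 21.05

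Power at exactly 21 per group is 79.9%. The plan's 21 is reproduced.

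**2. Which alpha was used?** With the same inputs and 80% power:

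| Alpha | n per group |
|---|---|
| two-sided 0.05 | 21.05 |
| one-sided 0.05 | 16.58 (17) |
| two-sided 0.5, the printed level | 6.16 (7) |

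Of these, only two-sided 0.05 gives 21. The printed <0.5 does not agree with the calculation in the same section.

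**3. Match the effect to the contrast.**

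| Component | Intervention | Control |
|---|---|---|
| Sensor (tracker) | yes | yes |
| Morning and evening reminders, 24 weeks | yes | yes |
| Payments, totaliser, progress messages, traffic-light calendar, first 12 weeks | yes | no |

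The cited 19 points are attached to the first two rows. The between-group difference comes from the third, for which the documents give no expected size.

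**4. What 25 or 21 evaluable per arm can deliver** (two-sample t-test, SD 22, two-sided 0.05). The 15- and 10-point rows are assumptions chosen to show the dependence; the documents give no basis for any particular increment.

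| Increment over reminders | Power, 25 per arm | Power, 21 per arm | n per arm for 80% |
|---|---|---|---|
| 19 points | 85% | 78% | 23 |
| 15 points | 66% | 58% | 35 |
| 10 points | 35% | 30% | 77 |

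Difference detectable with 80% power: 17.8 points at 25 per arm, 19.5 at 21.

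Expected 95% CI half-width = t × SD × √(2/n):
- 25 per arm: 2.011 × 22 × √(2/25) = 12.5 points
- 21 per arm: 2.021 × 22 × √(2/21) = 13.7 points

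**5. A conditional check on plausibility.** Suppose the 65% mean was observed without reminders (the documents do not say), reminders add the cited 19 points, and adherence is capped at 100%. Controls would then average 65 + 19 = 84%, leaving 100 − 84 = 16 points of headroom. A further 19-point difference in means could not occur. The finding does not depend on this, but it shows why the assumption needs a justification.

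**The case against.** The strongest reply is that this is a pilot. Section 7.2 says that no formal calculation is required and separately supports 25 per group by pilot-size guidance. Aims 2 and 3 are feasibility and data for a later power calculation. That stands as far as the number 50 is concerned. It does not rescue the power statement: having said that the size is based on a calculation with 80% power, the plan needs that calculation to fit its comparison, and aim 1 is effectiveness.

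Second, the label in the review is broad, and some tracker-type feedback (totaliser, messages, calendar) goes only to the intervention arm, so part of the 19 points might differ between arms. That is fair. The documents do not show how much of the 19 points is common to both arms; equally, they do not show that 19 points applies to the incentive package.

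Third, the sentence is correct as a conditional: if the difference is 19 points, power is about 80%. True, but the plan does not offer 19 points as a target or minimum important difference. It derives the figure from the tracker and reminder estimate.

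Fourth, the <0.5 is probably typographical and is a separate matter. The finding on the effect size holds without it. It is still the printed decision threshold and disagrees with the sample size in the same section, so it belongs in the same edit.

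**Conclusion.** The concern holds. The arithmetic is right, but its effect size comes from a different comparison, so the stated 80% power is not supported for incentives plus reminders against reminders alone. With SD 22 and two-sided 0.05, the trial has 80% power only for a difference of 17.8 points (25 evaluable per arm) to 19.5 points (21 per arm). At an assumed increment of 10 points, power would be 35% or 30%.

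These figures rest on the plan's SD, which comes from unpublished data at one hospital with reminder use not stated; on two-sided 0.05, inferred because it reproduces the 21; and on a t-test, although section 7.2 allows Mann-Whitney for non-normal data. They do not show that the true increment is small. The sample of 50 is not in question as a pilot size; the power claim and the printed significance level should be corrected.

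**What to change.** Reword section 7.2 as follows.

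- Keep 50 participants on the pilot-size guidance already cited.
- Remove the claim that the tracker or reminder effect gives 80% power for intervention against control.
- Put in its place a statement such as: *Both arms receive the tracker and reminders; this protocol does not assume a prior estimate of the added effect of the incentive package. With SD 22% and two-sided alpha 0.05 (t-test), 25 / 21 evaluable participants per arm give 80% power for a difference of 17.8 / 19.5 points and an expected 95% CI half-width of 12.5 / 13.7 points. For illustrative increments of 15 and 10 points, power is 66% / 58% and 35% / 30%.*
- Correct the printed significance level from <0.5 to two-sided 0.05.
- Report the between-group difference in adherence with its 95% confidence interval.

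If the sponsor has evidence for a particular increment over reminders, it could instead be stated with its source and the power given for it.

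The cost is rewording of one section, with no extra participants, visits or data. The power statement becomes conditional on the increment.

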#### 1.2. RATIONALE FOR CURRENT STUDY

In paediatric asthma, there are currently no randomised trials that explore the effectiveness of using financial incentives for improving medication adherence. A US proof-of-concept study that used electronic reminders coupled with financial incentives improved adherence to asthma medications in 12 African American adolescents. Participants were provided with a smartphone and an EMD (with associated App) to provide visual reminders, positive reinforcement (e.g., shooting a basket game and positive text messages when dose is taken) plus rewards (short-term: accessories to decorate personal app avatar and long-term: 1\$ per inhaler dose). Both adherence and asthma control (measured by the asthma control test ACT) improved across the 8-week period.

Similarly, a feasibility study conducted by ourselves found the use of financial incentives to be feasible and acceptable for improving adherence in paediatric asthma. Adolescents diagnosed with asthma, who had poor medication adherence (<80%) and poor asthma control were recruited from an outpatient asthma clinic. Twelve adolescents were invited to take part and 10 were recruited (7 males, 3 females, 12-16 years) to a 24-week intervention that consisted of eight weeks of electronic reminders and financial incentives related to their adherence (£1 per morning dosage, £1 per evening dosage, capped at £2 per day). Eight out of 10 adolescents provided adherence measurements up to the final study visit. Three adolescents successfully paired their mobile app and EMD up to the final study visit which was associated with improved adherence. The 7 adolescents unable to pair their mobile app and EMD had no change in adherence. Overall, adherence did not significantly change. Exit interviews with adolescents revealed reminders and incentives were welcomed but issues with the technology was frustrating. Adolescents also commented that the intervention was useful by promoting self-monitoring and increasing motivation to take medication.

These findings within asthma warrant the further exploration of this intervention design using financial incentives with the inclusion of a larger sample size and randomisation. In addition, to explore the potential mediators of sustained behaviour change, motivation and the key feature of habit, automaticity, will be tracked in this study.

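### The 80% power claim rests on an unstated dropout rate: 25 per group keeps about 80% only if loss stays below roughly 11–12%, and gives about 76% at the 20% loss seen in the team's own feasibility study

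*Combined protocol and SAP*

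**What the plan says.** Section 7.2 first says that a pilot does not need a formal sample size calculation, and then gives one. It takes an SD of 22 points from unpublished data on 400 children and a 19-point effect from a Cochrane review. The sample size is set "to give 80% power to achieve a 19% difference between the intervention group and controls", and the result is "21 participants are required per group. The target of 25 per group accounts for participant dropout". No dropout rate and no source for one appear. The section adds, as a separate support, guidance that 25 per group is enough for a pilot.

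The same section names Student's t test for normally distributed continuous data and the Mann-Whitney U test otherwise. On the test level it says "The significance levels for all tests will be set at <0.5", and it does not say whether tests are one- or two-sided.

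Section 1.2 describes the team's own 24-week feasibility study of the same kind of intervention and reports: "Eight out of 10 adolescents provided adherence measurements up to the final study visit". It also says that only three of the ten kept app and device paired to the final visit.

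**The concern.** The sentence on dropout assures the reader that 80% power survives expected loss. Nothing in section 7.2 lets the reader check that, and the one retention figure elsewhere in the document points to a larger loss than 25 per group allows for. The base figure of 21 also leaves no slack, because it is a rounded-down approximation rather than the number the planned test needs.

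The first aim in section 2.1 is effectiveness, so the power statement will be used when the result is read. A non-significant difference would be judged against 80% power when the trial may have had somewhat less. The third aim is to inform the power calculation of a definitive trial, and an undocumented retention assumption is a poor start for that.

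**Working it through.** **Inputs.** Difference 19 points, SD 22, power 80%, 21 required and 25 enrolled per group (section 7.2); 1:1 allocation (section 3); 8 of 10 with measurements to the final visit (section 1.2). Assumed: two-sided 5%. The printed level of 0.5, taken literally, gives 7 per group, and one-sided 5% gives 17. Two-sided 5% is the only choice tried that gives about 21.

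**Step 1: reproduce the 21.** Normal approximation, n = 2(z₀.₉₇₅ + z₀.₈₀)² × SD² / difference²:

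2 × (1.960 + 0.842)² × 22² / 19² = 21.05 per group.

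Rounded up this is 22; the plan's 21 is the same value rounded down. The figure is reproduced to within one participant.

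**Step 2: use the planned test.** With the noncentral t distribution and a standardised effect of 19/22 = 0.864, 80% power needs 22.05 per group, so 23. Power by number analysed per group:

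| Analysed per group | t test | Normal approximation |
|---|---|---|
| 25 | 84.9% | 86.3% |
| 23 | 81.7% | 83.4% |
| 22 | 79.9% | 81.7% |
| 21 | 78.0% | 79.9% |
| 20 | 75.9% | 78.0% |

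If the Mann-Whitney test is used instead (assumed efficiency 0.955), the requirement is 22.05/0.955 = 23.1 per group, and power at 20 is about 73.8%.

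**Step 3: the implied allowance.** 1 − 21/25 = 16%. The same 25 can fall to 22 with 12% loss (1 − 22/25) and to 23 with 8% loss (1 − 23/25).

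**Step 4: the loss on record.** 2/10 = 20%, exact 95% CI 2.5% to 55.6%. Then 25 × 0.80 = 20 per group, one fewer than the plan calls required.

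**Step 5: power against loss, from 25 per group.** Averaging the t-test power over random loss in each arm:

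| Loss | Mean power |
|---|---|
| 10% | 80.7% |
| 12% | 79.7% |
| 16% | 77.7% |
| 20% | 75.5% |
| 30% | 69.2% |

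Interpolating between 10% and 12%, power crosses 80% at about 10 + 2 × (0.7/1.0) = 11.4% loss. So about 80% holds up to roughly 11–12%. At the plan's own implied 16% it is about 78%.

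**Step 6: precision at 20 per group.** The standard error is 22 × √(2/20) = 6.96 points. With t₀.₉₇₅ on 38 degrees of freedom = 2.024, the expected 95% CI half-width is 2.024 × 6.96 = 14.1 points. The difference detectable with 80% power is 20.0 points.

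**The case against.** Three stronger readings are tempting, and the documents support none of them.

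- A reader might infer that 25 per group cannot deliver 80% power. It can: power is 84.9% with no loss and about 80% up to 11–12% loss. The shortfall is conditional on dropout.
- A reader might infer that 21 is a calculation error. It is the standard normal formula, rounded down, and differs from the t-test requirement by one or two per group.
- A reader might infer that 20% is the loss to expect for the primary outcome. It is 2 of 10 children and cannot be told apart from 16%. It counts measurements up to a 24-week visit, whereas section 3.1 names no analysis window for the primary outcome. Data are also downloaded at 12 weeks, and section 4.4 keeps and uses data collected before withdrawal, so loss for a 12-week analysis could be lower. The feasibility participants were outpatient-clinic attenders with poor adherence and poor control, whereas this trial recruits after emergency attendance.

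The uncertainty also runs the other way. Section 3 routes adherence data through the paired app, and seven of the ten feasibility participants could not pair app and device, so loss could exceed 20%. The plan does not say how partial records enter the primary analysis, so they cannot be counted in support of the dropout claim as written.

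It is also fair to say that this is a pilot, that pilot guidance is cited as a second basis for 25 per group, and that the choice of effect matters more than a few points of power. At 14.47 points, the lower confidence limit quoted in section 7.2, power with 20 per group is 53%. These points limit the importance of the finding. They do not supply the missing dropout rate.

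**Conclusion.** The concern holds in a limited form. Section 7.2 claims 80% power after dropout without stating a dropout rate. For the planned t test, power is 78.0% at the stated 21 per group and about 76% if loss matches the 20% in the feasibility study, a shortfall of about 2 to 4 percentage points. The claim is sound only if loss is no more than roughly 11–12%, and nothing in the document supports a rate that low.

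This rests on an assumed two-sided 5% level, the plan's own 19 points and SD of 22, and loss that is similar in both arms and unrelated to outcome. It is a minor-to-moderate correction of a stated figure, with no bearing on whether 50 is a sensible size for a pilot. It does not settle whether a 19-point effect, taken from trials of trackers or reminders, applies to a comparison in which both arms receive reminders.

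**What to change.** Keep 50 participants. In section 7.2:

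1. State the assumed loss and its source, and say which period it refers to (12 or 24 weeks).
2. Remove the unqualified statement that 25 per group covers dropout at 80% power, and replace it with text such as: *With 25 per group, power for a 19-point difference (SD 22, two-sided 5% t test) is 85% with no loss, 78% with 16% loss and 76% with 20% loss, as in our feasibility study. With 20 per group, the difference detectable at 80% power is 20 points and the expected 95% CI half-width is 14 points.*
3. Correct the printed significance level and state the sidedness, so that the calculation can be reproduced from the text.

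The cost is a few lines in one section and a slightly less favourable power figure, with no added participants and no change to the analysis. For comparison, holding 80% power at 20% loss would need 23/0.80 = 28.75, so 29 per group (58 in total) for the t test, or 21/0.80 = 26.25, so 27 per group (54) from the plan's own base. For a pilot, the restatement is the proportionate choice.
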